3.11 TREATMENT ASSESSMENT AND RESPONSE (FOLLOW UP PERIOD)

- Because of the nature of peritoneal imaging and because cytoreductive surgery will likely eliminate all imageable disease, response can only be measured in terms of radiographic disease-free survival. At any time point when there is evidence of progressive disease (imageable tumor nodules or increasing ascites persistent on CT scans as interpreted by the official interpretation of the imaging studies) the patients will be scored as progressive disease. In some cases this may require successive scans, but the time of

recurrence will be retrospectively defined at the point the first scan demonstrated imageable disease.

- Patients will be evaluated 3 months from the operative date (+/- 1 month) intervals for the first year; every four months for (+/- 1 month) the next year and then q 6 months (+/- 1 month) thereafter.
- The following evaluations will be performed at each visit:
 - Imaging studies
 - Physical examination to include ECOG, weight and vital signs
 - Tumor markers as indicated
 - CBC, acute care, mineral and hepatic panel, CRP, Albumin, pre-albumin, ferritin, Hgb A1c if elevated pre-op.
 - Completion of Health related Quality of Life Forms (HRQOL) – at the first follow up visit and then at each evaluation until off study.
- Patients who are unwilling or unable to return for follow up evaluation will be followed every 6 months by phone contact until off study criteria are met. The following information may be obtained:
 - Summary of treatment received since the previous contact
 - Estimation of ECOG status
 - Request for imaging studies, physical exam and laboratory reports to be sent to the PI

Note: if patient is taken off study prior to 1 year following surgery, the HRQOL will be completed at the off study evaluation if possible.

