3.10 POST DISCHARGE

- CBC weekly following discharge or until toxicities have resolved (less than grade 3 or baseline) and patient has recovered from nadir. This may be done through the patient's referring physician with the results faxed to [name] or her designee.
- Patients will return to clinic approximately 4-8 weeks following surgery for their 1st post-operative visit and will be followed as clinically indicated until recovery. Upon recovery from the surgical procedure, the following end of treatment evaluations will be performed:
 - Imaging studies to establish new baseline
 - Tumor markers as indicated
 - CBC, acute care, mineral and hepatic panel, CRP, Albumin, pre-albumin, ferritin, Hgb A1c if elevated pre-op.
 - Physical examination to include ECOG, weight and vital signs
 - QOL survey

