8 STATISTICAL CONSIDERATIONS

The primary objective of this trial is to conduct a pilot study to determine if the use of debulking surgery and HIPEC in patients with intra-peritoneal spread of adrenocortical carcinoma is able to be associated with an intra-peritoneal progression free interval which may exceed that of the use of chemotherapy alone.

Data from a recently published study indicated that a 5.0 month median PFS¹⁴ may be attained in similar patients using EDP and mitotane. This will be a single arm trial with the goal of seeing if the proposed combination of HIPEC and surgery may be associated with a 10 month median PFS. Using the method of Brookmeyer and Crowley³³, the study will plan to enroll 24 fully evaluable patients over a 60 month period. Based on this method, with 24 subjects, there would be 80% power to determine if there is a median PFS of 10 months rather than 5 months, based on a one-tailed 0.10 alpha level test. In practice, Kaplan-Meier curves and appropriate confidence intervals at selected time points will be provided to help interpret the results relative to historical results.

At the rate of 6 patients per year, 24 evaluable patients could be enrolled in 5 years, allowing for a ceiling of 30 patients to account for patients who may be inevaluable.

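### Perfusion flow (3.5 versus 10.1.4) and thiosulfate timing (3.6 versus 10.2.4) contradict each other; as a lesser point, 3.11 gives the 3.10 baseline scan no role in scoring progression

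*Combined protocol and SAP*

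**What the plan says.** **Perfusion.** Section 3.5 keeps the flow at roughly 1.0 L/min, as tolerated, for 90 minutes. Section 10.1.4 adds cisplatin to a circuit running at 1.5-2 L/min.

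**Thiosulfate.** Section 3.6 first has the infusion start just before the perfusion and run for 12 hours overall. It then has a 20-minute loading dose start when cisplatin enters the circuit, followed by 25.56 g/m² at 2.13 g/m² per hour for 12 hours. Section 10.2.4 starts the loading dose just before cisplatin, again with 12 hours of maintenance.

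**Progression.** Section 3.11 scores progressive disease on "imageable tumor nodules or increasing ascites persistent on CT scans", and the time of "recurrence will be retrospectively defined at the point the first scan demonstrated imageable disease". Its premise is that "cytoreductive surgery will likely eliminate all imageable disease". On timing it says: "Patients will be evaluated 3 months from the operative date (+/- 1 month) intervals for the first year".

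Section 3.10 separately obtains "Imaging studies to establish new baseline". It says "Patients will return to clinic approximately 4-8 weeks following surgery for their 1st post-operative visit" and then "Upon recovery from the surgical procedure, the following end of treatment evaluations will be performed", so the scan itself has no fixed date. Section 3.11 does not refer to that scan.

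**Design.** Section 8 compares the single arm with a 5.0-month historical median PFS and states that "there would be 80% power to determine if there is a median PFS of 10 months rather than 5 months".

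**The concern.** The perfusion is the treatment under test. If the implementation section and the pharmacy section disagree on flow and on when thiosulfate starts, two teams could both follow the protocol and deliver different procedures. A deviation could then not be judged against a single standard.

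The 3.11 rule raises a different, smaller problem. Ascites must be increasing to count, but a nodule need only be visible. HIPEC goes ahead at a completeness of cytoreduction (CC) score of 0 or 1, and CC-1 in Appendix D allows residual nodules under 2.5 mm. If such a nodule showed on a scan and stayed the same, the wording would score it as recurrence. The 3.10 scan, obtained as a new baseline, would have no part in the decision. The endpoint affected is the primary one, and there is no control arm in which the same misclassification would occur.

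**Working it through.** **1. Flow** (3.5 and 10.1.4)
- 3.5: 90 min × 1.0 L/min = 90 L circulated.
- 10.1.4: 90 × 1.5 = 135 L, and 90 × 2 = 180 L.
- The 10.1.4 rate is 1.5 to 2 times the 3.5 rate. The qualifiers in 3.5 (roughly, as tolerated) do not plausibly stretch that far.

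**2. Thiosulfate duration** (3.6)
- The plan's own maintenance figure reproduces: 25.56 / 2.13 = 12.0 h.
- Load plus maintenance: 20 min + 12 h = 12 h 20 min, against 12 h overall in the same section.
- If 12 h were the whole infusion, maintenance would last 11.667 h and deliver 11.667 × 2.13 = 24.85 g/m². The difference is 25.56 − 24.85 = 0.71 g/m², or 2.8% of the maintenance amount.

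**3. Thiosulfate start**, side by side
- 3.6, first statement: just before the perfusion.
- 3.6, second statement: with the addition of cisplatin.
- 10.2.4: just before cisplatin.

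Section 3.5 warms the cavity to at least 40 °C before the perfusion clock starts, so the start of perfusion and the addition of cisplatin need not coincide. The warm-up time is not stated, so the gap cannot be sized.

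**4. The planning figure in section 8**
- Assume exponential PFS and no censoring. With a 10-month median, S(5) = 0.5^(5/10) = 0.707, tested against 0.50 with n = 24 and one-sided alpha 0.10.
- Power = Φ[((0.707 − 0.5) × √24 − 1.2816 × 0.5) / √(0.707 × 0.293)] = 79.4%.
- The stated 80% is reproduced.

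**5. When a stable visible nodule would be dated under 3.11**
- At the 3.10 scan, if done at the 4-8 week visit: 28/30.44 = 0.92 months to 56/30.44 = 1.84 months.
- At the first 3.11 visit: 3 ± 1 = 2 to 4 months.
- On schedule, both fall before the 5-month median. Such a patient would count as a failure by 5 months whatever the true course of the disease.

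**6. Direction.** Counting stable residual as an event can only bring events forward. The opposite rule, treating everything on the 3.10 scan as baseline, could absorb early regrowth and lengthen PFS. The two rules therefore err in opposite directions.

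**The case against.** On the perfusion sections, the case against is that the conflicts are editorial. No section ties litres circulated to outcome, starting just before cisplatin and starting with cisplatin are nearly the same, and the duration gap is small. This is fair as to size, but it does not give the flow rate or the start time a single value. A reader might also cite the description in 1.2.3 of a bolus 20 minutes before cisplatin as a further conflict. That sentence describes earlier trials, so it is not counted here.

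On 3.11 the objection is stronger:
- The section deliberately chooses radiographic disease-free survival, under which any visible tumour is an event.
- Treatment is limited to CC 0 or 1, and nodules under 2.5 mm may often be invisible.
- The rule relies on the official imaging interpretation and allows successive scans.
- Ablated lesions are a weak example: 2.1.1 admits disease amenable to ablation, but 3.4 describes no ablation step.
- The silence of section 6 on the CC score proves little, since it names no progression date either.

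Most of this stands and limits the point to a clarification. Two things remain. A stable residual nodule is also persistent, so that word does not exclude it. And the baseline scan still has no stated use in scoring.

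A reader might go further and ask that residual disease documented by the surgeon be excused until it grows, as the primary rule. The documents do not show that this is needed. In an unblinded single arm with no growth threshold, it would make the endpoint depend on what the surgeon recorded.

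**Conclusion.** The flow and thiosulfate instructions are wrong as written, because they cannot all be followed. The flow figures differ by a factor of 1.5 to 2. The thiosulfate duration differs by 20 minutes (2.8% of the maintenance amount), and the difference in start time cannot be sized from the documents. No view is taken on which value or timing is right.

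The 3.11 gap is real but secondary. It matters only if residual disease after CC-1 surgery is visible, stable and read as tumour. The documents give no frequency for this; given the size limit, it is probably low. When it happens, the event falls at about 1-4 months, assuming visits are on schedule, and biases PFS downwards.

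A reader might infer that the trial is underpowered, or that the rule could produce a false positive. Neither is supported. Any loss of power depends on a share of affected patients that would have to be assumed, and the direction is against the treatment. The 24 patients and 80% power are not disputed. The difference between the 1 cm residual limit (Precis, 3.4) and CC 0/1, and the mixed use of CC and CCR, are editorial: the CC 0/1 condition is the stricter one and governs HIPEC and evaluability.

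**What to change.** - **Perfusion and thiosulfate.** The investigators reconcile 3.5 with 10.1.4 on flow, and 3.6 both internally and with 10.2.4 on thiosulfate start and total duration, so that each perfusion has one instruction. This costs amendment wording only.
- **Progression rule.** State in 3.11 whether the 3.10 scan is the reference for progression, and how tumour visible on that scan is scored.
- **Data.** Record the CC score on the case report form.
- **Analysis.** Report intraperitoneal PFS two ways: with any imageable nodule as an event, and with only new or growing disease relative to the 3.10 scan as an event. Because the two err in opposite directions, close agreement would show that the choice does not matter.

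The cost of the last three items is a few sentences, one form field and one extra analysis. The 3.10 scan is already obtained, so no patients or procedures are added. The 1 cm and CC/CCR wording can be tidied in the same amendment.

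### For patients who do not return to clinic, outside imaging is requested at 6-monthly calls but neither required nor given an interval, so progression can be recorded later or less completely than for attending patients

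*Combined protocol and SAP*

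**What the plan says.** Section 3.11 makes the outcome radiographic. Progression is scored from imaging, and recurrence is dated back to the first scan that showed disease.

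There are two follow-up routes.

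- **Clinic.** "Patients will be evaluated 3 months from the operative date (+/- 1 month) intervals for the first year", then every 4 months in year 2 and every 6 months after that, with the same one-month window. Imaging is a fixed part of each visit.
- **Phone.** Patients unwilling or unable to return "will be followed every 6 months by phone contact until off study criteria are met". A list of what may be collected at the call includes "Request for imaging studies, physical exam and laboratory reports to be sent to the PI". The list is permissive, gives no scan interval, and does not require a local scan to be done.

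Not returning to clinic is not in itself an off-study criterion (section 3.13.2). Evaluability depends only on successful debulking and HIPEC (section 3.1). Phone-followed patients therefore stay on study and count among the 24.

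Section 8 compares the result with "a 5.0 month median PFS" from a published chemotherapy trial and aims for 10 months. It gives no censoring rule and no rule for missed or irregular scans.

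**The concern.** The trial has one arm and is judged against a fixed historical median, so a delay in detecting progression is not balanced by a control arm. It simply lengthens recorded PFS. For attending patients the protocol fixes when scans happen. For patients on the phone route it does not, so the date of progression depends on whatever a local physician happens to order and send.

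Year 1 contains both the 5-month benchmark and the 10-month target, and it is the period in which the clinic schedule is densest. That is where unequal ascertainment matters most. Because section 8 has no censoring rule, it is also open whether a phoned but unscanned patient is counted as progression-free to the last call or censored at the last scan.

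**Working it through.** **1. The plan's own figure.** Inputs from section 8: null median 5 months, target 10 months, 24 patients, one-sided alpha 0.10, Brookmeyer-Crowley method. Under exponential PFS (assumed), the test compares S(5) = 0.5 with S(5) = 0.5^(5/10) = 0.707.

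Power = Φ{[(0.707 − 0.5)·√24 − 1.2816·0.5] / √(0.707·0.293)} = Φ(0.374/0.455) = 79.4%.

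This reproduces "there would be 80% power to determine if there is a median PFS of 10 months rather than 5 months". In exact binomial terms, the rule is to reject if at least 16 of 24 are progression-free at month 5, with alpha 0.076 and power 75.1%. The result therefore turns on recorded status at month 5.

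**2. Recorded month-5 PFS with no treatment effect.** Assume a true 5-month median, scans exactly on schedule, no deaths, and average prognosis on both routes. Let k of 24 be phone-followed; k is not in the documents, so 2, 4 and 6 are used.

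- Attending patient: last scan before month 5 is at month 3, so recorded S(5) = S(3) = 2^(−3/5) = 0.660.
- Phone patient with no scan before month 6: recorded S(5) = 1.
- Phone patient with one post-operative scan at about 1.5 months on which progression is scored: recorded S(5) = 2^(−1.5/5) = 0.812. Section 3.10 plans a visit at about 4–8 weeks, with imaging on recovery.
- Phone patient scanned locally on the 3.11 schedule, with reports retrieved: 0.660, the same as an attending patient.

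Mixture: [(24 − k)·0.660 + k·q]/24, where q is the phone patients' recorded S(5).

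| k | q = 1 | q = 0.812 | q = 0.660 |
|---|---|---|---|
| 0 | 0.660 | 0.660 | 0.660 |
| 2 | 0.688 | 0.672 | 0.660 |
| 4 | 0.716 | 0.685 | 0.660 |
| 6 | 0.745 | 0.698 | 0.660 |

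**3. Separating the phone route from ordinary visit spacing.** The 3-monthly schedule alone moves recorded S(5) from 0.50 to 0.660. To remove that part, set the null so that attending patients have recorded S(5) = 0.5 (that is, true S(3) = 0.5, a true median of 3 months). Then apply the rule of at least 16 of 24.

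- No scan before month 6: the k phone patients always count as progression-free, so the false-positive rate is P[Bin(24 − k, 0.5) ≥ 16 − k]. This is 0.08 for k = 0, then 0.14, 0.25 and 0.41 for k = 2, 4 and 6.
- Scan at 1.5 months: phone patients have recorded S(5) = 2^(−1.5/3) = 0.707. P[Bin(24 − k, 0.5) + Bin(k, 0.707) ≥ 16] is 0.10, 0.13 and 0.17.
- Local scans on schedule and retrieved: 0.08 throughout.

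**4. Delay per patient.** If phone patients are scanned only every 6 months (assumed), the mean lag from true to recorded progression is 3.4 months, against 1.8 on the clinic schedule, at a true median of 5. At a true median of 10 it is 3.2 against 2.0.

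**5. Sample median.** In simulation under the 6-monthly assumption and a true median of 5, the mean sample median moves from 6.7 months (k = 0) to 6.8, 6.9 and 6.9 (k = 2, 4, 6). The effect is concentrated at month 5.

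**The case against.** There are good points in the plan's favour, and most of them limit the size rather than remove the gap.

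- A reader might infer that these patients are followed by phone alone. They are not: imaging, examination and laboratory reports are requested at the call.
- A reader might infer that the 6-monthly call sets the progression date. It does not. A local scan at month 3, retrieved at month 6, gives a month-3 event. Only the local scan interval matters, and calling more often would not by itself help.
- A reader might infer that every phone-followed patient appears progression-free at month 5. The post-operative imaging in section 3.10 undercuts that, which is why the table has a second column.
- A reader might infer that early progression is lost. On a 6-monthly scan interval it is delayed: recorded progression by month 6 is the same on both schedules (56% at a true median of 5). It is lost only if no scan is done or sent, which the text allows.
- The contrast with attending patients is less sharp than 6 months against 3. The one-month windows allow gaps of up to 5 months between year-1 scans (month 2 to month 7), and after year 2 the clinic schedule is itself 6-monthly.
- It is plausible that patients unable to travel are doing worse, but the documents do not say so, and the same provision covers those who are merely unwilling.

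What remains is that nothing in section 3.11 secures local scans at the clinic intervals for patients who still count toward the primary endpoint.

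**Conclusion.** The point holds as a gap in how the primary endpoint is ascertained. One route has scheduled, required imaging; the other has optional imaging with no interval. The direction favours the treatment.

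The size cannot be fixed from the documents. For 2 to 6 phone-followed patients of 24, recorded month-5 PFS rises by about 0.03 to 0.09 with no scan before month 6, by about 0.01 to 0.04 with one scored scan at 1.5 months, and by nothing if local scans follow the schedule and are retrieved. These figures rest on exponential PFS, exact visit times, no deaths and equal prognosis on both routes. If phone-followed patients do worse, the distortion could be larger.

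The documents do not support reading this as the main source of any overstatement of PFS. The scheduled visit spacing accounts for the larger shift (0.50 to 0.660), the sample median barely moves, and how progression was assessed for the historical 5.0 months is not stated. The gap is nevertheless worth closing, because it is cheap to close and bears on the month-5 test.

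**What to change.** In section 3.11, for patients who do not return:

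- State that CT will be requested locally at the same intervals as clinic visits.
- State that the images will be obtained and read under the same rule as clinic scans, with progression dated to the first positive scan.
- For imaging, replace the permissive 'may' with a firm 'will be requested'.
- Record each patient's follow-up route.

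In section 8, as a sensitivity analysis only, report PFS with these patients censored at their last adequate scan. State that this censoring may be informative: if those who stop attending are sicker, it also inflates PFS. An interval-censored analysis, which uses the actual scan dates, is preferable as an addition.

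The cost is a few extra contacts and image transfers per patient, plus any local CT that would not otherwise have been done. Local scan timing will not be fully under the sponsor's control, so some irregularity will remain.

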3.12 MEASUREMENT OF HEALTH RELATED QUALITY OF LIFE

Baseline Quality of Life Questionnaires (QOL) will be completed prior to the surgical procedure during the first follow up visit [following recovery from the surgical procedure] approximately one year following the procedure or at the time off study.

Patients will be informed of the details of the QOL part of this study and reassured that their decision to participate will not affect their participation in the protocol. Once enrolled, the patient has the right at any time to elect not to continue completing the questionnaires. In the event a patient goes off study prior to completion of the follow up time points, the data gathered from their completed QOL questionnaires will be included in the final analysis.

Measures will be initially administered by the Associate Investigator Research Nurse or designee prior to randomization. The Research Nurse will assess the patient's ability to read, and if the patient is unable to read, it will not be administered. The Research Nurse or designee will administer the questionnaires providing a firm surface at a table or a clipboard and a pencil. The patients will be directed to complete the questionnaires using the following instructions:

We would like to better understand how you and other persons in this study feel, how well you are able to do your usual activities, and how you rate your health while you are participating in this research study. To help us better understand these things about you and other persons participating in this study please complete this questionnaire about your quality of life. This questionnaire should not take longer than 15 minutes to complete.

The questionnaire is simple to fill out. Be sure to read the instructions on the top of the questionnaire. Remember, this is not a test and there are no right or wrong answers. Choose

the response that best represents the way you feel. I will quickly review the questionnaire when you are done to make sure that all the items have been completed. Please answer all the items with the response that is most applicable.

You should answer these questions by yourself. Your husband/wife or other family members or friends should NOT assist you in completing the questionnaire. Please fill out the questionnaire now. Return the questionnaire to me when you have completed it. We will be asking you to complete this again during some of your follow up visits. If you have any questions, please ask.

Once the patient has completed the questionnaire, the Research Nurse or designee, will review it for completeness and thank the patient for their cooperation. Subsequent measurements will be administered by the Associate Investigator Research Nurse, or designee, when the patient returns for follow-up visits as specified in section 3.11.

The Research Nurse or designee will request that the patient complete the questionnaire prior to seeing the physician, as the interaction between the patient and physician may influence the patient's answers to the questionnaire. In the event a patient is taken off study, patients will be asked to complete one last questionnaire (as appropriate to the point of withdrawal) and the data will be included in the analysis.

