1.1.2 Secondary Objectives

- Determine morbidity of this procedure in this patient population
- Determine the impact of surgery and HIPEC on QOL
- Determine the impact of surgery and HIPEC on hormone excess
- Examine patterns of recurrence (local versus systemic)
- Perform molecular analyses to try to discern if there are intrinsic differences between tumors that recur widely throughout the peritoneal surface and those that metastasize to other organs or are confined to a local recurrence.
- Determine overall survival after optimal debulking and heated intraperitoneal chemotherapy with cisplatin in patients with intraperitoneal spread of adrenocortical cancer.

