1.2.5 Surgical metastasectomy

Surgical metastasectomy has been used extensively for ACC in our institution. Our published data and experience demonstrates the ability to safely perform this surgery and to prolong disease free interval to greater than a year in selected patients³². Combining surgery with Cisplatin, the drug most effective in ACC, seems like a logical direction for the treatment of this histology where the bulk of tumor is intraperitoneal. The purpose of this trial is to determine if an aggressive surgical approach with intraperitoneal administration of heated cisplatin when tumor volume is minimal, can impact and improve on progression free survival.

Given the aggressive treatment regimen and the aggressive nature of the diseases, it is important to understand the impact this therapy has on patients' health related quality of life. As a secondary endpoint we will therefore evaluate patients' health related quality of life prior to therapy and at intervals following recovery from the surgery and HIPEC. The goal of tracking quality of life is while surgery may temporarily negatively impact on QOL, it is our hope that it would rebound to better than pre-op if this approach has any merit and utility in the care of patients in the future.

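### Patients followed by phone have no planned QOL collection between the early forms and the off-study form, so later QOL is likely to over-represent patients able to travel

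*Combined protocol and SAP*

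**What the plan says.** Section 1.1.2 lists a secondary objective: "Determine the impact of surgery and HIPEC on QOL". Section 1.2.5 gives the expected course: QOL may fall for a time after surgery, but "it is our hope that it would rebound to better than pre-op".

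After baseline, section 3.12 has the research nurse or a designee give the form "when the patient returns for follow-up visits as specified in section 3.11". It describes an in-person sitting with a table or clipboard and pencil. No postal, telephone or electronic mode appears anywhere.

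Section 3.11 asks for the form "at the first follow up visit and then at each evaluation until off study". It then adds a second pathway: "Patients who are unwilling or unable to return for follow up evaluation will be followed every 6 months by phone contact". Three items are listed for that contact: treatment since the last contact, "Estimation of ECOG status", and a request for outside imaging, examination and laboratory reports. QOL is not among them.

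Other text also bears on the point:
- Section 3.10 includes a QOL survey among the evaluations made on recovery: "Patients will return to clinic approximately 4-8 weeks following surgery for their 1st post-operative visit".
- Section 3.12 asks for one last questionnaire when a patient is taken off study. The note at the end of 3.11 asks for it, where possible, from patients who leave before one year. Neither states a mode.
- Section 3.12 keeps completed forms in the final analysis.
- Section 8 gives no QOL analysis and no method for missing QOL data.

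**The concern.** Patients on the phone pathway are still on study and still being contacted, yet the plan lists no QOL collection for them at those contacts. The form is self-completed and takes about 10 minutes (Appendix C), or at most 15 (section 3.12), so length is not an obstacle.

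Inability to return is plausibly linked to poor function. If so, forms are missing for a reason related to the outcome. The rebound question depends mainly on forms completed well after recovery from surgery, and those are the forms lost. A mean change from the remaining patients would lean toward showing a rebound. With 24 evaluable patients and no planned sensitivity analysis, a reader of the results could not tell how much of an apparent rebound came from who was still attending.

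**Working it through.** **Step 1: what a phone-followed patient can still contribute.** Take a patient who attends the 4-8 week visit and then stops returning.

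| Occasion | Section | Route for this patient |
|---|---|---|
| Baseline | 2.2.2, 3.12 | Completed before surgery |
| First post-operative visit, on recovery | 3.10 | Usually completed in clinic |
| Each later evaluation | 3.11 | None listed |
| About one year | 3.12 | None listed |
| Off study | 3.11 note, 3.12 | Requested; mode not stated |

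How much is lost depends on the timetable. Three-monthly visits in year one (3.11) mean forms at 3, 6, 9 and 12 months, so four are lost. Section 3.12 instead sets a form "approximately one year following the procedure or at the time off study", so mainly one is lost. The two timetables differ and should be reconciled separately; the one-year form is exposed under both.

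**Step 2: possible size.** The plan gives no QOL figure to reproduce. Its one power statement (section 8) concerns PFS and does not enter here. The following inputs are assumptions, not taken from the documents:
- f, the share not returning: 0.20 or 0.30
- d, how much lower non-returners' follow-up QOL is: 0.5 or 1.0 SD
- rho, the correlation between baseline and follow-up: 0.5
- no off-study form recovered

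From section 8, n = 24 evaluable.

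Overstatement of the mean paired change = f x (gap in change between returners and non-returners).
- Case A, equal mean baselines: the gap in change is d, so the bias is f x d.
- Case B, missingness follows follow-up QOL, so non-returners' baselines are lower by rho x d: the gap is (1 - 0.5) x d, so the bias is 0.5 x f x d.

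SE of the paired change = sqrt(2 x (1 - 0.5)) / sqrt(n observed) = 1 / sqrt(n observed). With f = 0.20, 24 x 0.8 = 19.2, taken as 19, giving SE 0.229. With f = 0.30, 24 x 0.7 = 16.8, taken as 17, giving SE 0.243.

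| f | d (SD) | Bias A (SD) | A / SE | Bias B (SD) | B / SE |
|---|---|---|---|---|---|
| 0.20 | 0.5 | 0.10 | 0.44 | 0.05 | 0.22 |
| 0.20 | 1.0 | 0.20 | 0.87 | 0.10 | 0.44 |
| 0.30 | 0.5 | 0.15 | 0.62 | 0.075 | 0.31 |
| 0.30 | 1.0 | 0.30 | 1.24 | 0.15 | 0.62 |

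**Step 3: sensitivity.** Widening the inputs to f = 0.10-0.40 and d = 0.3-1.0 SD gives 0.1 x 0.3 = 0.03 to 0.4 x 1.0 = 0.40 SD in case A, and half of that, 0.015 to 0.20 SD, in case B.

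**Step 4: effect on a test, for scale only.** Suppose the true change is zero and a one-sided 0.10 test were applied. The chance of a positive result is 1 - Phi(1.2816 - bias/SE). In table order this is 20%, 34%, 25% and 48% in case A, and 14%, 20%, 17% and 25% in case B, against a nominal 10%.

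**The case against.** A reader might infer that phone-followed patients give no QOL data, or that the objective is answered only in patients well enough to travel. The documents do not support either reading. Such patients have a baseline form and usually a first post-operative form, and completed forms stay in the analysis. Phone follow-up continues until an off-study criterion is met, at which point one last form is requested, and nothing says that it needs a clinic visit.

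That exit route could matter. Off-study criteria include progression needing systemic therapy. Under exponential PFS, 24 x 0.5^(12/10) = 10.4 patients would be progression-free at 12 months with a 10-month median, and 24 x 0.5^(12/5) = 4.5 with a 5-month median. Off-study forms could therefore supply a substantial share of late data.

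The direction of bias is also inferred. The phone group includes people who are simply unwilling, and the plan gives neither its size nor its health status. The contact list is permissive and does not bar QOL collection. Supervised completion without family help is a deliberate choice, and the questionnaires are voluntary.

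Finally, a reader might take the 48% error rate as the finding. It needs equal baselines in returners and non-returners, and it borrows a one-sided 0.10 level that section 8 sets only for PFS. No QOL test is planned.

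These points narrow the concern but do not remove it. The off-study form is triggered by exit rather than by time since surgery. Before one year, the 3.11 note asks for it only where possible, and it may fail after death or loss to follow-up. A patient still on study by phone at one year has no stated route to the one-year form. The 4-8 week form comes too early to carry the rebound question.

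**Conclusion.** The gap is real and limited. Scheduled follow-up QOL is collected at clinic visits, and the phone contact lists no QOL item. Apart from the early forms and one off-study form of unstated mode, patients who do not return have no planned QOL collection while on study. Later QOL is therefore likely, though not certain, to favour patients able to travel.

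The size cannot be derived from the documents. Under the stated assumptions the overstatement is about 0.05-0.15 SD (0.2-0.6 standard errors) if non-returners started lower, and up to 0.10-0.30 SD (0.4-1.2 standard errors) if they started level. Recovered off-study forms could reduce it, as would a larger share of non-returners who are merely unwilling. The point concerns one secondary objective and leaves the primary PFS analysis untouched. It is worth correcting because the correction is inexpensive.

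**What to change.** - **Section 3.11:** add the FACT-C to the phone-contact items, mailed before each six-monthly contact for self-completion and return with the same written instructions. Time one mailing to the one-year point.
- **Section 3.12:** change the clause "when the patient returns for follow-up visits as specified in section 3.11" to read *at each time point, in clinic or by mail, as specified in section 3.11*. State that the off-study form may also be completed by mail.
- **Data collection:** record the mode of completion and the reason for any missing form.
- **Analysis:** report the paired change from baseline with and without the mailed forms.

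The cost is a wording amendment, postage and two extra data items. Staff already plan to phone these patients, and section 9.6.1 already combines mailed documents with a telephone call for re-consent. The drawback is a mixed mode of administration, with less control over whether the form is completed unaided and no check for completeness on the spot. Recording the mode and reporting both analyses lets the reader judge that trade-off.
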